5.3.1.2 Causality

By convention, all events reported at the injection site (either solicited or unsolicited) will be considered as related to the administered product and then referred to as reactions. In a same way, all solicited systemic events pre-listed in the CRF are also considered as related to vaccination and will be considered as reactions. Missing causality for unsolicited non-serious AEs and SAEs will be considered at the time of analysis as related to vaccination.

5.3.1.3 Measurements

Partially missing temperatures will be handled as described in [Section 4.4.1.1.1](#).

5.3.1.4 Intensity

For solicited reactions, missing intensities will be handled as described in [Section 4.4.1.1.1](#). For unsolicited non-serious AEs, missing intensities will remain missing and will not be imputed.

5.3.1.5 Start Date and Stop Date

Missing or partially missing start dates for unsolicited AEs will remain missing and not be imputed. If either the start or stop date is missing or partially missing, the time of onset will be considered to be missing. Nevertheless, unsolicited AEs with missing time of onset will be included in analyses according to the visit collected.

Missing or partially missing stop dates for AEs (solicited reactions and unsolicited AEs) will remain missing and not be imputed.

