4.4.1.2 Unsolicited Adverse Events

Unsolicited AEs include non-serious unsolicited adverse events (AEs), immediate unsolicited AEs, serious adverse events (SAEs), adverse events of special interest (AESIs), and medically-attended adverse events (MAAEs). Analysis for unsolicited AEs only include those AEs collected within 21 days after each injection. SAEs, AESIs, and MAAEs collected out of this range will only be presented in the analysis of SAEs, AESIs, and MAAEs.

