4.4.1.2.4 Time of Onset

Time of onset is derived from the start date of the unsolicited AE provided in the clinical database and the date of last vaccination as described in [Section 4.4.1.2.3](#):

Time of Onset = start date of the unsolicited AE – date of last vaccination before the unsolicited AE + 1

The time of onset should be considered as missing only if one or both of the dates are missing or partially missing.

The unsolicited AEs will be analyzed “Within 21 days”, which corresponds to AEs with a time of onset between 1 and 22 days or missing.

An AE with missing time of onset will be considered to have occurred just after the vaccination indicated by the visit number in “Appeared after visit” or similar filed, so will be included in these tables.

Time of onset will be displayed as follows:

- D01-D04
- D05-D08
- D09-D15
- D16 or later
- Missing

Note: To further clarify the analysis,

- Any unsolicited AEs collected throughout the study (SAEs, MAAEs, or AESIs) with time of onset > 22 days after each injection will not be presented in tables of unsolicited AEs within 21 days but only in tables of SAEs, MAAEs, or AESIs.
- Any unsolicited AEs (planned to report up to 21 days) with time of onset between 1 and 22 days or missing after each injection will be presented in the tables of unsolicited AEs within 21 days.
- Any unsolicited AEs (planned to report up to 21 days) with time of onset > 22 days after each injection will not be presented in any tables but listed separately.
- Any unsolicited AEs with null (0) or negative time of onset will be excluded from the above tables and listed separately.

Main safety analysis will include only those unsolicited AEs with time of onset before a participant received a non-study authorized/approved COVID-19 vaccine if applicable. Events with time of onset on or after the date of receiving a non-study authorized/approved COVID-19 vaccine will be listed separately.

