4.4.1.3 SAEs

SAEs will be analyzed throughout the study using the following periods:

- Within 21 days after each injection
- During the study (ie, all SAEs occurred during the entire study or the cutoff date which corresponds to the date of any interim analysis)

Note: SAE that occurred before vaccination (negative time of onset) will not be included in analysis but will be listed separately.

Main safety analysis will include only those SAEs with time of onset before a participant received a non-study authorized/approved COVID-19 vaccine, if applicable. SAEs with time of onset on or after the date of receiving a non-study authorized/approved COVID-19 vaccine will be listed separately.

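### SAP 5.3.1.5 blanks an adverse event's time of onset when only its stop date is missing, contradicting 4.4.1.2.4 and making late unresolved events eligible for the 21-day tables

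*SAP*

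**What the plan says.** SAP 4.4.1.2.4 (Time of Onset) gives the derivation: "Time of Onset = start date of the unsolicited AE – date of last vaccination before the unsolicited AE + 1". It then limits when the result may be missing: "The time of onset should be considered as missing only if one or both of the dates are missing or partially missing". The two dates in question are the event's start date and the last vaccination date. The stop date is not an input.

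SAP 5.3.1.5 (Start Date and Stop Date) gives a different condition: "If either the start or stop date is missing or partially missing, the time of onset will be considered to be missing". It also keeps events with missing onset in the analyses, assigned by the visit at which they were collected, and leaves missing stop dates unimputed.

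The conflict matters because of how 4.4.1.2.4 defines the 21-day tables, "which corresponds to AEs with a time of onset between 1 and 22 days or missing". An event with missing onset is treated as having happened just after the vaccination that the visit field points to.

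The SAP says twice that late serious, special-interest and medically attended events stay out of those tables. In 4.4.1.2.4, those with onset beyond day 22 "will not be presented in tables of unsolicited AEs within 21 days but only in tables of SAEs, MAAEs, or AESIs". In 4.4.1.2, "SAEs, AESIs, and MAAEs collected out of this range will only be presented in the analysis of SAEs, AESIs, and MAAEs".

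**The concern.** For an event with a complete start date and no stop date, one section returns a number and the other returns missing. The word *only* in 4.4.1.2.4 means that 5.3.1.5 cannot be read as adding to it. The start-or-stop condition is the one that 4.4.1.2.5 gives for duration, so 5.3.1.5 looks like the duration rule attached to the wrong variable. It sits in the missing-data section, where a programmer would look for such a rule.

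Protocol Table 3.1 makes unsolicited adverse events up to 21 days after each injection a primary safety endpoint. If the data contain an event with no complete stop date and an onset outside days 1 to 22, programmers working from different sections could produce different 21-day tables.

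The exposed events are mainly unresolved SAEs, MAAEs and AESIs, because Protocol 8.4.4 collects other unsolicited events only to 21 days. AESIs include new-onset chronic conditions, which SAP 4.4.1.5.7 requires to be expected to last at least 3 months. The study was also cut to 6-month safety follow-up, leaving less time for late events to resolve.

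Other uses of onset could be affected:

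- Ongoing events that truly began within the window would lose a known onset category.
- Section 4.4.1.2.4 relies on onset to remove events dated before vaccination: "Any unsolicited AEs with null (0) or negative time of onset will be excluded from the above tables and listed separately". Section 4.4.1.3 does the same for SAEs: "SAE that occurred before vaccination (negative time of onset) will not be included in analysis but will be listed separately".
- The cut-off at receipt of a non-study COVID-19 vaccine is also worded in terms of onset.

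**Working it through.** The plan has no figure to reproduce. The check applies both rules as written to the same events, then works out what one misplaced event does to a table row.

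**Rules compared**

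- Rule A (SAP 4.4.1.2.4): onset = start − last vaccination + 1; missing only if one of those two dates is incomplete.
- Rule B (SAP 5.3.1.5): missing if the start or the stop date is incomplete; otherwise the same formula.
- Table membership (SAP 4.4.1.2.4): onset from 1 to 22, or missing.

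**Illustrative events, all with complete start and vaccination dates**

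| Event | Rule A onset | In 21-day table? | Rule B onset | In 21-day table? |
|---|---|---|---|---|
| Day 5, resolved | 5 | yes | 5 | yes |
| Day 5, ongoing | 5 | yes | missing | yes |
| Day 22, ongoing | 22 | yes | missing | yes |
| Day 23, ongoing | 23 | no | missing | **yes** |
| Day 41, resolved | 41 | no | 41 | no |
| Day 41, ongoing | 41 | no | missing | **yes** |
| Day 150, ongoing | 150 | no | missing | **yes** |
| Onset 0 (before vaccination), ongoing | 0 | no | missing | **yes** |

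The rules differ only when there is no complete stop date. Table membership changes only when the true onset lies outside 1 to 22.

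**In study days.** On the two-injection schedule with the second injection on D22, an unresolved event starting on D100 has onset 100 − 22 + 1 = 79 under Rule A and is excluded. Under Rule B it is missing and therefore eligible. On the one-injection schedule the same start gives 100 − 1 + 1 = 100 under Rule A, and missing under Rule B.

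**Effect of one misplaced participant.** Planned sizes are from Protocol Table 4.3. SAP 5.1.1.2 calls for summaries by intervention group and age group. The participant is assumed not to be counted in that row already.

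- Vaccine arm: 1/44 = 2.3 percentage points. Placebo arm: 1/22 = 4.5.
- Vaccine arm by age group: 1/24 = 4.2 and 1/20 = 5.0.
- Placebo arm by age group: 1/12 = 8.3 and 1/10 = 10.0.
- Sentinel pooled with Cohort 2 at one dose level (also SAP 5.1.1.2): 5 to 25 Sentinel participants (Protocol Table 4.2) plus 44 gives 49 to 69, so 1/49 = 2.0 down to 1/69 = 1.4.

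With the SAP's Clopper-Pearson interval, a row in a 44-person arm moves from 0/44 (0%, 95% CI 0 to 8.0) to 1/44 (2.3%, 95% CI 0.06 to 12.0).

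**The case against.** The best defence is that 4.4.1.2.4 is the dedicated derivation section. It gives the formula, restricts missingness explicitly and adds clarifying bullets; 4.4.1.2 repeats the intent, and 4.4.1.2.3 also works from the start date. To program 5.3.1.5, one would have to override all of that for one sentence that reads like a slip. The detailed programming may sit in the separate tables, listings and figures document, which is not available here.

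Further points limit the reach:

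- No affected event has been shown. How the CRF records the stop date of an ongoing event is not visible, and Protocol 8.4.6 has related events followed to resolution, stability or chronicity.
- Missing-onset events are placed by the visit field. For a D100 event the preceding visit is not a vaccination visit, so entry into a 21-day table is possible but not certain.
- The cut-off at a non-study COVID-19 vaccine can be read as a comparison of calendar dates, which a known start date still supports. Before the first injection only procedure-related SAEs are collected.
- Misplaced events would be visible in the missing-onset category and remain in the whole-study SAE, AESI and MAAE tables. The summaries are descriptive, and development had been discontinued before this SAP version.

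These points stand as limits on size and likelihood. The pre-vaccination and cut-off effects should be treated as possible only. None of this reconciles the two sections, and a reader cannot tell from the SAP which rule the tables follow.

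**Conclusion.** The concern holds. Section 5.3.1.5 contradicts 4.4.1.2.4 and is wrong as written: applied literally, it makes late unresolved SAEs, AESIs and MAAEs eligible for tables that the SAP itself bars them from.

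The practical effect rests on three things the documents leave open: which section is programmed, whether ongoing events carry no stop date, and how the visit field maps to an injection when the visit is not a vaccination visit. The number of affected events therefore cannot be stated. The per-participant shifts above use planned denominators; enrollment stopped early, so shifts in individual arms could be larger.

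This should be corrected, but the harm is moderate. Apart from the COVID-19 harm test, the safety analyses are descriptive.

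**What to change.** Replace the sentence in SAP 5.3.1.5 with two statements. First, onset is missing only when the event's start date or the last vaccination date is incomplete, with a cross-reference to 4.4.1.2.4. Second, an incomplete stop date makes duration missing, as in 4.4.1.2.5, and leaves onset unchanged. Then confirm that the table programs follow 4.4.1.2.4.

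Under that wording, the unresolved events at days 23, 41 and 150 and at onset 0 in the worked table are excluded again, and those at days 5 and 22 stay in with a known onset.

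The cost is one sentence of SAP text. If 5.3.1.5 has already been programmed, the onset derivation for unsolicited events must be corrected and the 21-day tables rerun. No new data are needed.

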5.3.2 Immunogenicity

No test or search for outliers will be performed.

5.3.3 Laboratory Safety

No imputation of missing values and no search for outliers will be performed.

For the computation of descriptive statistics, a value reported as:

- “< X” will be converted to a value of $0.5 * X$,
- “≥ X” will be replaced by the X

If a participant has a missing baseline then the data for this participant will be included in the category “missing at baseline” in the table taking into account the baseline status.

5.3.4 Additional Immunological Tests

- If a value is < LLOQ, then use the computed value $LLOQ/2$
- If a value is between $\geq LLOQ$ and $< ULOQ$, then use the value
- If a value is $\geq ULOQ$, then use the value of ULOQ

5.3.5 Efficacy

Missing data will not be imputed. No test or search for outliers will be performed.

5.4 Interim / Preliminary Analysis

A preliminary interim analysis was performed on safety and immunogenicity including pseudovirus neutralizing antibody and binding antibody (ELISA) data collected up to D43 for participants enrolled into the Sentinel Cohorts. Database was cleaned with a partial database lock

conducted. After that, the clinical team decided to terminate further vaccination and enrollment, and all enrolled participants were to be unblinded, thus allowing each of them to make an informed decision as to whether they want to receive an authorized COVID-19 vaccine.

The remaining interim analyses that have been specified in protocol will no longer be performed as the development of the mRNA COVID-19 has been discontinued and the study enrollment and vaccination has been interrupted.

Participant safety will be continuously monitored by the Sponsor's internal safety review committee which includes safety signal detection at any time during the study (see also Section 8.4.1 of the protocol for Sentinel Cohort dose escalation, Section 8.4.2 of the protocol for CS-ESDR details, and Section 8.4.3 of the protocol for halting rules for the entire study).

5.5 Determination of Sample Size and Power Calculation

No formal power calculations have been performed. The sample size was determined based on logistical considerations and common practices for first-in-human trials

The study targets enrollment of approximately 333 participants 18 years of age and older, including the 5 participants already vaccinated in the low-dose group. The actual number of participants enrolled will depend on which dose-level groups are allowed to be evaluated in the Sentinel Cohort and the Full Enrollment Cohort. The number may be higher if Expanded Sentinel Cohorts are Exercised for all dose-level, and if all dose-levels progress to the Full Enrollment Cohort (maximum number of study participants approximately 383); conversely, the number may be lower if not all the dose-levels are evaluated in the Sentinel Cohort or/and not all the dose-levels progress to the Full Enrollment Cohort. A subset of up to 77 randomly selected participants in Cohort 2 will be included in an AIT subset. Please refer to Table 4.2 and Table 4.3 of the protocol for the planned sample size in Sentinel Cohort and Full Enrollment Cohort.

5.6 Data Review for Statistical Purposes

A review of the data will be led by data management before database lock. This review of the data included statistical review.

5.7 Changes in the Conduct of the Trial or Planned Analyses

The content of the current SAP is based on protocol v3.0 and the following modifications.

When conducting the planned preliminary interim analysis, as the sensitivity of the rapid diagnostic test (RDT), used to assess seropositivity at screening, was low, an ad hoc analysis set "mFAS" was defined as a subset of the FAS that excludes participants with positive pseudovirus neutralization test results against SARS-CoV-2 D614G variant at baseline. In addition, due to 8 participants in the Sentinel Cohort with dosing errors related protocol deviations, immunogenicity analyses were performed using "mFAS" according to the study intervention participants actually received. The "mFAS" by injection group will also be used in the final analysis.

After the planned preliminary interim of the Sentinel Cohort participants, a decision to discontinue the development of the mRNA COVID-19 vaccine was made. On September 27, 2021, all Investigators were informed to terminate further vaccinations and enrollment. All

enrolled participants were to be unblinded to allow them to make their decision to receive an authorized COVID-19 vaccine. All clinical sites were to contact participants to inform them of the discontinuation of further study vaccinations, told what intervention they received and invited to come in for an unscheduled visit for counseling to answer any questions about the study, to discuss available options for receipt of an approved /authorized COVID vaccination, and were requested to provide unscheduled blood draw for serological assessment (UBXX). Participants were informed that additional D22 or D36 blood draws for serological assessment would be appreciated but are not mandatory. No protocol defined schedule visits or blood draws at timepoints later than D36 were required. Monitoring for SAEs, AESIs, medically attended AEs, and pregnancy and collection of influenza and COVID-19 vaccines were continued with safety calls. On March 15, 2022, after concurrence from regulatory authorities, Investigators were notified of the decision to end the study at the 6-month safety follow-up instead of 12-month follow-up.

As the further development of the mRNA COVID-19 vaccine was terminated and as mentioned above in [Section 5.4](#), interim analyses initially planned in the protocol will not be performed. The final analysis will be conducted in an unblinded manner.

In addition, the following analyses planned at the time of the protocol or previous version of SAPs will not be performed:

- Between groups ratios of neutralizing Ab GMTs and between group seroconversion rates differences
- Between groups ratios of anti-S antibody concentrations and between group seroconversion rates differences
- Correlated of risk and of vaccine efficacy
- Complementary analysis and sensitive analysis on immunogenicity data and safety data
- Safety and immunogenicity analyses by aggregated groups

Detailed analyses can be found in the SAP document of Tables, Listings and Figures.

6 References List

4. Newcombe RG. Two-sided confidence intervals for the single proportion: comparison of seven methods. *Stat Med.* 1998;17(8):857-72.
5. Agresti, Alan (2002). *Categorical Data Analysis (Second ed.)*. Wiley. ISBN 0-471-36093-7.
